#### 5.2 Primary Safety Objectives

- The evaluation of all adverse events including device related, procedure related and additional serious adverse events.
- Evaluation and reporting of additional surgical intervention at the operative site including revision and/or device removal

All adverse events will be documented on a continuous basis and reviewed by the Bone and Joint Clinical Research Staff. Information regarding all device failures including implant breakage, subsidence, migration, or expulsion will be captured.

### 5.3 Secondary Objectives

Secondary objectives are expected to further define the patient outcomes for effectiveness of the surgery and device in this population.

#### 5.3.1 Oswestry Disability Index

The Oswestry Disability Index (ODI) is the most commonly used outcome measure in patients with low back pain. It has been extensively tested, showed good psychometric properties, and applicable in a wide variety of settings. This validated patient-reported outcome measure is a 10 item questionnaire that evaluates disability and functional impairment associated with back problems. A total ODI score is determined by adding the scores of the individual questions and dividing that total by the maximum possible score to yield a percentage. Therefore, the ODI score ranges from 0% to 100%. A higher score corresponds to a greater disability.

#### 5.3.2 Visual Analog Scale

The severity of back and leg pain will each be evaluated in all study subjects using a 10 cm visual analog scale (VAS).

## 6. Study Enrollment and Follow Up Visits

### 6.1 Screening visit

Consecutive patients who potentially meet the inclusion/exclusion criteria for the study will be screened for eligibility. Patients who agree to participate in the study will sign an IRB approved Informed Consent form. Consenting patients who meet the inclusion/exclusion criteria will complete preoperative demographics and subject

questionnaires (ODI and VAS). Patients will have recent (appropriate for surgical planning by the PI) AP, Lateral and Flex/Ext x-rays.

## 6.2 Follow Up Visits

Patients will return to clinic to complete subject questionnaires (ODI and VAS) at 2 weeks, 3 months, 6 months, and 12 months postoperatively. Plain radiographs (AP and Lateral views) will be obtained at 2 weeks, 6 months and 12 months. A CT scan will also be obtained at 12 months.

# 7. Hospitalization/Surgical Technique/Discharge

Subjects will be admitted to the hospital according to the Principle Investigator's standard for an instrumented posterolateral fusion in conjunction with a TLIF surgery. Prophylactic antibiotics, preoperative planning, patient positioning and anesthesia will be carried out in accordance with the institution's and Investigator's standard of care.

## 7.1 Surgical Approach

The surgeon performs a midline incision and standard posterior exposure to decorticate the transverse processes bilaterally to accommodate graft for the posterior fusion. The spinous processes and interspinous ligaments can usually be left intact, which minimizes epidural scarring and provides a larger surface area for the posterior fusion.

After exposure, pedicle screws are placed bilaterally. Fluoroscopy or other strategies may be used to aid in proper screw positioning. Distraction may then be performed using the surgeon's preferred method to open the posterior portion of the disc space, if needed.

## 7.2 Transforaminal Lumbar Interbody Fusion (TLIF)

For the TLIF procedure, access to the disc space is gained via a triangular working window. The window is formed by the traversing nerve root and thecal sac on the medial side, the exiting nerve root from the proximal vertebral level on the lateral side, and the superior aspect of the pedicle of the distal vertebra forms the base of the triangle. The surgeon performs a laminotomy, laminectomy and/or facetectomy (partial or total) along with removal of the ligamentum flavum to provide access to the disc space. Care should be taken to preserve the facets as much as possible and remove only enough bone as needed to provide access for introduction of the interbody spacer and to decompress and mobilize the nerve root as necessary. If decompression of the contralateral side of the spinal canal is required, the TLIF procedure can be modified to include a central laminectomy.

After exposure of the posterior aspect of the disc, an incision is made in the annulus through which the discectomy and endplate preparation are performed. Endplate preparation consists of removal of the cartilaginous endplate down to bleeding bone. The Titanium PL interbody cage is then introduced.

Once the interbody implant is in place and bone graft added to the disc space, distraction is released and compression is applied to the pedicle screw to load the anterior implant and restore lordosis to the spine.

## 7.3 Surgical Close and Recovery

Standard procedures and precautions are to be followed for closure of the surgical incision and postoperative recovery. The patient is typically mobilized out of bed the day after surgery; bracing is not required but can be used according to

surgeon preference. The subject may be instructed to return to normal activity at the discretion of the Investigator.

## 8. Data Collection

All data collected for the study will be maintained on Case Report Forms and stored in a secure location at the Bone and Joint Clinic of Baton Rouge. All data will also be stored in discreet fields in a database.

8.1 Baseline Data – A preoperative history and physical to include demographics and diagnosis data will be taken at the screening/baseline visit after Informed Consent is obtained. Baseline data will include:

- Date of Visit
- DOB
- Gender
- Height and Weight
- Tobacco Use
- Diagnosis
- Affected levels
- AP, Lateral, and Flex/EXT x-rays
- Back and Leg VAS
- ODI

8.2 Surgery Data.

- Implanted System Details
- Surgery Detail/Concomitant Procedures
- Surgery Time (initial incision to closure)

- Perioperative Antibiotic Use
- Estimated Blood Loss
- Intra-operative complications, if any

### 8.3 Follow up data

- AP, Lateral x-rays (2 weeks, 6 weeks and 12 months)
- Back and Leg VAS (2 weeks, 6 weeks, 3 months and 12 months)
- ODI (2 weeks, 6 weeks, 3 months and 12 months)
- CT (12 months)
- Adverse Events (if applicable)

## 9. Benefits and Risks

### 9.1 Potential Benefits

There is no guarantee that the subject will experience any immediate or direct benefits from the surgery, the Tritanium ® device or from taking part in this study.

### 9.2 Risks

Potential risks include those associated with any spinal surgery resulting in neurological, cardiovascular, respiratory, gastrointestinal compromise, or death.

### 9.3 Mitigation of Risks

Operative and acute periprocedural risks for the patients enrolled in this study are mitigated by the operating orthopedic spine surgeon being trained and experienced in the proper surgical technique to perform the surgery and to implant the respective device. Long-term risks such as device failure or pseudoarthrosis are mitigated by proper patient selection and by following accepted standard of care in this population for spinal fusion surgery.

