## 2. Study Hypothesis

The Titanium PL cage will produce satisfactory fusion rates due to its highly porous material designed for bone in-growth and biologic fixation. TLIF fusion rate, adverse events and patient reported outcomes will be qualitatively comparable to PEEK results in the literature.

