## 3. Study Methods

### 3.1 Study Design

Prospective, non-randomized (single arm) single-center study to evaluate the post-operative radiographic and patient outcome variables of the Titanium PL cage compared to literature reported outcomes for traditional PEEK cage for interbody fusion treatment of degenerative disc disease (DDD).

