### 3.3 Primary Study Endpoint

## Fusion status at 1 year

### 4. Study Population

#### 4.1 Sample size

20 patients will be enrolled in the study. Outcomes from this pilot study may be used to design larger controlled trials.

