#### 4.2 Inclusion and Exclusion Criteria

Patients must meet all of the inclusion criteria and none of the exclusion criteria in order to be eligible to enter the study.

- Inclusion Criteria
  - Subject has one or more of the following diagnoses:
    - Degenerative disc disease (DDD) at one level or two contiguous levels from L2 to S1.
    - DDD may also include up to Grade I spondylolisthesis at the involved level(s).
    - Note: DDD is defined as back pain of discogenic origin with degeneration of the disc confirmed by history and radiographic studies.
    - Degenerative scoliosis for which the Titanium PL cage will be used as an adjunct to fusion.
    - Skeletally mature and  $\geq 18$  years old at time of enrollment
    - Completed at least 6 months of non-operative therapy prior to surgery
    - Willing and able to sign a study specific consent and comply with the requirements of the protocol including follow up visits and imaging.

- Exclusion Criteria
  - >2 levels requiring surgical intervention
  - Non-degenerative pathology including tumor, trauma, post-laminectomy kyphosis
  - Psudeoarthrosis at the index level
  - Previous fusion at the levels to be treated or at adjacent level
  - Any abnormality present which affects the normal process of bone remodeling including, but not limited to, severe osteoporosis involving the spine, bone absorption, osteopenia, primary or metastatic tumors involving the spine, active infection at the site or certain metabolic disorders affecting osteogenesis.
  - History of osteoporotic fracture
  - History of an endocrine or metabolic disorder known to affect bone and mineral metabolism
  - Inadequate tissue coverage over the operative site or taking medications that may interfere with bony/soft tissue healing including chronic steroid use
  - Known allergy to titanium or cobalt chrome or may be sensitive to materials
  - Rheumatoid arthritis or other autoimmune disease or a systemic disorder such as HIV, active hepatitis B or C or fibromyalgia
  - Lumbar kyphosis- lumbar lordosis < 20°

- Degenerative scoliosis  $>20^\circ$  OR any other pathology scoliosis (idiopathic, congenital, posttraumatic, iatrogenic)
- Active systemic infection or infection at the operative site
- Marked local inflammation
- Any open wounds
- Pregnant, or intends to become pregnant during the study
- Current smokers

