## 10. Statistical Methods

The purpose of this study is to build upon the available data for the Tritanium implant in this on-label population. Descriptive statistics will be used to summarize demographics and baseline and surgical variables.

Change in in VAS and ODI will be determined and the percentage of patients exceeding the MCIC (minimally clinical important change) will be reported for each outcome. The MCIC to be used for each patient reported outcome are derived from Parker, et al, *J Neurosurgery Spine*, 2011.

- VAS – Leg pain- 2.8
- VAS – Back Pain- 2.1
- ODI – 14.9

The fusion rate will be reported and qualitatively compared to TLIF fusion rates in the literature.

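### The fusion rate is compared with literature that need not share this study's eligibility, so neither similarity nor difference can be credited to the cage or its porous material

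*Combined protocol and SAP*

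**What the plan says.** Section 3.1 describes a "Prospective, non-randomized (single arm) single-center study" whose comparator is published results for PEEK cages. Section 10 says the fusion rate will be "qualitatively compared to TLIF fusion rates in the literature". It gives no benchmark rate, no rule for choosing series, no date by which they must be chosen, and no matching or adjustment for case mix.

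Section 2 hypothesises that the cage "will produce satisfactory fusion rates due to its highly porous material designed for bone in-growth and biologic fixation". It also expects fusion, adverse events and patient-reported outcomes to be comparable, in a qualitative sense, to PEEK results in the literature.

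Section 4.2 narrows the population in ways that bear on bone healing. One criterion is "Any abnormality present which affects the normal process of bone remodeling including, but not limited to, severe osteoporosis involving the spine, bone absorption, osteopenia", and it goes on to certain metabolic disorders. Another is "Current smokers". The list also covers:
- previous osteoporotic fracture, and endocrine or metabolic bone disease;
- drugs that may impair healing, including chronic steroids;
- autoimmune disease;
- pseudoarthrosis at the index level, and previous fusion at the index or an adjacent level;
- BMI above 40, or overweight judged to threaten the fixation or the device.

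Section 9.3 states that "Long-term risks such as device failure or pseudoarthrosis are mitigated by proper patient selection" and names standard of care as a second mitigator.

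On the use of the results, Section 4.1 says: "20 patients will be enrolled in the study. Outcomes from this pilot study may be used to design larger controlled trials".

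**The concern.** The protocol itself treats patient selection as something that lowers pseudoarthrosis, which is the failure side of the primary endpoint. Its only comparison is with outside series, and it does not ask whether those series admitted smokers, patients with poor bone quality or patients with earlier fusions. A rate close to the literature could then reflect the cage, the choice of patients, or a mixture in which one hides the other. Section 2 nevertheless gives the cage material as the reason for a good rate.

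At stake is what the study may conclude. Its stated hypothesis is comparability with PEEK, and a favourable case mix can produce that impression by itself. Limiting the benchmark to PEEK series would not solve this, because a PEEK series can also differ in case mix.

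**Working it through.** The plan has no figure to reproduce: 20 patients are given without a target rate, precision or power, and no literature fusion rate is stated. The arithmetic below is therefore illustrative.

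**Inputs.** From the documents: 20 patients (Section 4.1). Assumed, with no source in the documents:
- N, the literature non-union rate;
- p, the share of literature patients who would be excluded here;
- RR, the relative risk of non-union in that share.

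**Formula.** Let n0 be the non-union rate among literature patients who would have been eligible here. Then N = (1 − p)·n0 + p·RR·n0, so n0 = N / (1 − p + p·RR). The shift produced by selection alone is N − n0.

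| N | p | RR | 1 − p + p·RR | n0 | Shift (points) | Patients of 20 |
|---|---|---|---|---|---|---|
| 10% | 25% | 2 | 0.75 + 0.50 = 1.25 | 8.0% | 2.0 | 0.4 |
| 15% | 40% | 2.5 | 0.60 + 1.00 = 1.60 | 9.4% | 5.6 | 1.1 |
| 5% | 20% | 2 | 0.80 + 0.40 = 1.20 | 4.2% | 0.8 | 0.2 |
| 15% | 40% | 3 | 0.60 + 1.20 = 1.80 | 8.3% | 6.7 | 1.3 |
| any | 0 | any | 1.00 | N | 0 | 0 |
| any | any | 1 | 1.00 | N | 0 | 0 |

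The first two rows give the range of about 2 to 6 points. The next two are the ends of a wider grid (N 5–15%, p 20–40%, RR 2–3). The last two show when the shift vanishes: the literature was selected alike, or the excluded features carry no extra risk.

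**Reading the factor.** In the first two rows, a cage with 1.25 or 1.60 times the comparator's non-union in like patients would be expected to match the literature exactly (8.0% × 1.25 = 10%; 9.375% × 1.60 = 15%).

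**Against sampling error.** One patient in 20 is 5 points. With 18 of 20 fused (90%), the exact 95% interval is 68.3% to 98.8%, far wider than any shift in the table.

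**Direction.** The formula covers only patients whom this study leaves out. Sections 3.2 and 4.2 also admit two-level disease, and Section 4.2 admits degenerative scoliosis up to 20°. If a comparison series were limited to one level, or had no scoliosis, and those features raise non-union, its case mix would push the other way.

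**The case against.** The strongest reply is that nothing in the documents shows how the cited series chose their patients. A reader might infer that the literature was selected less strictly, so that the comparison must favour this cage. The documents do not support that: the series may have used similar exclusions, and the two-level and scoliosis patients admitted here could pull in the opposite direction. This part of the objection stands. What can be said is that comparability is neither shown nor required.

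A second reply is that this is a 20-patient pilot case series with a qualitative comparison, no test, no margin and no claim of superiority. That also stands, and it limits how serious the point is. It does not remove the point, because comparability is the hypothesis and the causal wording in Section 2 goes beyond description.

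Third, sampling error is larger than any plausible shift. That is true, but a case-mix bias does not shrink with more patients, and a confidence interval does not reveal it.

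Fourth, Section 9.3 is a general risk statement that credits standard of care too. Agreed: it is supporting evidence, and the gap itself lies in Sections 10 and 2.

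Finally, readers might judge comparability afterwards. Section 8.1 would help with tobacco use, height, weight and affected levels, but it lists no bone-quality measure. Choosing series once the result is known also leaves room for a favourable choice.

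**Conclusion.** The point holds as a gap in the comparison. The plan neither requires nor reports similar eligibility in its literature benchmark, so its fusion rate cannot be attributed to the cage or the porous material, whichever way it falls. A single arm without a control cannot isolate a material effect in any case.

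The size and net direction of any bias are unknown. The figure of about 2 to 6 points in this study's favour rests wholly on assumed values of N, p and RR, and it is zero if p = 0 or RR = 1.

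Two further inferences go too far. One is that the same bias enters a planned literature comparison of ODI and VAS: Section 2 mentions such comparability, but Section 10 plans only change scores and the share of patients exceeding the minimal important change. The other is that the rate will mislead the later trial. That would need a trial enrolling more broadly, which the documents do not say.

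This limits interpretation. It does not undermine the study as a descriptive case series.

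**What to change.** In Section 10:
- Name the comparison series before the first 12-month CT is read.
- Tabulate how each series handled smoking, bone quality, BMI, healing-impairing drugs, metabolic or autoimmune disease, prior fusion, number of levels and scoliosis, beside this study's criteria.
- Base the comparison on the series, or reported subgroups, with the closest eligibility. If none is close, state that the comparison may favour this study and cannot by itself support a conclusion of comparability with PEEK.

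Matching on only one or two items, such as smoking and previous index-level fusion, would not be enough, because it leaves most of the exclusions unaddressed.

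In Section 2, delete the clause that credits fusion to the porous material and its bone in-growth design, and limit the conclusion to the selected population.

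The cost is a short literature table, possibly fewer usable series, and a more cautious conclusion. Eligibility, treatment and visits do not change.

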## 10. Statistical Methods

The purpose of this study is to build upon the available data for the Tritanium implant in this on-label population. Descriptive statistics will be used to summarize demographics and baseline and surgical variables.

Change in in VAS and ODI will be determined and the percentage of patients exceeding the MCIC (minimally clinical important change) will be reported for each outcome. The MCIC to be used for each patient reported outcome are derived from Parker, et al, *J Neurosurgery Spine*, 2011.

- VAS – Leg pain- 2.8
- VAS – Back Pain- 2.1
- ODI – 14.9

The fusion rate will be reported and qualitatively compared to TLIF fusion rates in the literature.

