## 1. Introduction

### 1.1 Study Purpose

To evaluate the fusion rate and clinical outcomes at 1 year of 20 patients with DDD who undergo a 1 or 2 level TLIF with Tritanium® PL cage and pedicle screw fixation. The proposed case series will build on the body of clinical and radiological evidence for this implant in TLIF patients. It will also provide pilot data for future studies that will compare the Tritanium ® cage to PEEK.

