### 1.3 Device

Tritanium ® PL is an intervertebral body fusion device indicated for use with autograft and/or allogenic bone graft comprised of cancellous and/or corticocancellous bone graft when used as an adjunct to fusion in patients with degenerative disc disease (DDD) at one level or two contiguous levels from L2 to S1. The Tritanium ® PL cage is a 3D manufactured titanium cage designed with angled serrations for bidirectional fixation and to maximize surface area for endplate contact with the implant. The cage is also designed to address the potential for subsidence into the endplates.

The Tritanium® PL Cage was cleared for marketing under 510(k) K160955

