### 3.2 Treatment Group

20 patients requiring an open 1 or 2 level TLIF will make up the study population. Eligible patients will have lumbar (L2-S1) degenerative disc disease (may have up to grade 1 spondylolisthesis), and/ or degenerative scoliosis. DDD is defined as back pain of discogenic origin with degeneration of the disc confirmed by history and radiographic studies. The DDD patients may also have up to Grade I spondylolisthesis at the involved level(s). These patients should be skeletally mature and have six months of non-operative therapy.

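### The plan names one on-label DDD cohort, but eligibility also admits degenerative scoliosis without DDD, so the single pooled fusion rate may not describe the population it is named for

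*Combined protocol and SAP*

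**What the plan says.** The population is described in six places.

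- **Section 1.1** states the purpose in terms of "20 patients with DDD who undergo a 1 or 2 level TLIF". **Section 3.1** likewise describes interbody fusion treatment of DDD.
- **Section 1.3** gives the only statement of the device's indication in the documents: an "adjunct to fusion in patients with degenerative disc disease (DDD) at one level or two contiguous levels from L2 to S1". Scoliosis is not mentioned. The section cites a 510(k) number but does not reproduce the clearance.
- **Section 3.2** defines the treatment group as lumbar DDD, possibly with low-grade spondylolisthesis, "and/ or degenerative scoliosis".
- **Section 4.2** opens the inclusion list with "Subject has one or more of the following diagnoses" and gives as a separate entry "Degenerative scoliosis for which the Titanium PL cage will be used as an adjunct to fusion". The exclusions remove degenerative scoliosis above 20 degrees and scoliosis of any other type.
- **Section 10** says the study is to "build upon the available data for the Tritanium implant in this on-label population". It plans one fusion rate, compared qualitatively with published TLIF rates, and the share of patients exceeding a threshold change on VAS and ODI. No outcome is planned by diagnosis.

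Section 8.1 lists diagnosis among the baseline data.

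**The concern.** The eligibility rules and the population labels do not describe the same patients. Under Sections 3.2 and 4.2 a patient with mild degenerative scoliosis and no DDD may be enrolled, and no cap on the number of such patients is stated. Under Sections 1.1, 3.1 and 10 the results would be presented as coming from a DDD, on-label cohort.

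Fusion at 1 year is the primary endpoint. There is no control arm, so the rate is interpreted only against the literature, and Section 1.1 intends the data as a pilot for later comparisons with PEEK. Both uses depend on knowing whom the rate describes. If scoliosis-only patients are enrolled, a reader of the report could not recover the rate for the DDD patients from what Section 10 promises.

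**Working it through.** **Step 1: who can enter.** Section 4.2 requires every inclusion criterion to be met, but its diagnosis criterion is met by any one listed diagnosis. Degenerative scoliosis is its own entry and carries no DDD requirement. The wording of Section 3.2 treats it as an alternative to DDD as well as a possible addition, so it cannot be read only as a form of DDD. The protocol also defines DDD separately, as discogenic back pain with confirmed disc degeneration, and the scoliosis entry does not have to meet that definition. Degenerative scoliosis of up to 20 degrees without DDD is therefore eligible.

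**Step 2: does the label cover everyone who can enter?** The indication as written in Section 1.3 names DDD only, as do Sections 1.1 and 3.1. On the documents' own text, neither label is established for a scoliosis-only patient.

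**Step 3: would the planned analysis show the difference?** Section 10 summarises baseline variables, so the mix of diagnoses could be visible. Fusion, VAS and ODI are not planned by diagnosis.

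**Step 4: how far could the pooled rate move?** The plan states no expected fusion rate, so there is no figure of its own to reproduce. The inputs are:

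- N = 20 (Section 4.1);
- k scoliosis-only patients (assumed);
- DDD fusion of 90% (assumed);
- scoliosis-only fusion between 60% and 90% (assumed).

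The formulas are:

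- pooled rate = [(20 - k) × DDD rate + k × scoliosis-only rate] / 20
- shift = pooled rate - DDD rate

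| k | Pooled rate, scoliosis-only fusion 60% | Pooled rate, scoliosis-only fusion 90% | Shift from DDD rate |
|---|---|---|---|
| 0 | 90% | 90% | 0 |
| 2 | (18 × 0.90 + 2 × 0.60)/20 = 87% | 90% | 0 to -3 points |
| 5 | (15 × 0.90 + 5 × 0.60)/20 = 82.5% | 90% | 0 to -7.5 points |

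If the two rates are equal, the shift is zero whatever the mix.

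**Step 5: comparison with sampling error.** For 18 of 20 fused (90%), the exact (Clopper-Pearson) 95% interval is 68.3% to 98.8%. With few scoliosis-only patients, the assumed shift is small beside that width.

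**The case against.** The strongest reply has four parts.

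*Section 1.3 may be only a summary of the clearance.* The scoliosis entry in Section 4.2 uses the same adjunct-to-fusion language as Section 1.3, so Section 10 could be right and Section 1.3 incomplete. This stands. A reader might infer that the trial enrols off-label patients. The documents do not support that, because the clearance text is not in them. Even so, Sections 1.1 and 3.1 would still describe a narrower population than Sections 3.2 and 4.2.

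*The comparator is TLIF in general.* Section 10 compares with published TLIF rates, and Section 1.2 describes TLIF as treating a range of degenerative conditions. This also stands. A reader might infer that a mixed cohort invalidates the literature comparison, but the plan does not tie that comparison to DDD alone. What suffers is the name attached to the rate.

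*Nothing shows that fusion differs by diagnosis.* That is correct. A reader might infer that the pooled rate will be biased by a known amount. No such amount can be derived, and the exclusions limit how different these patients can be.

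*All enrolled patients are a legitimate main summary for a descriptive pilot.* This is accepted. A reader might infer that the headline should be restricted to DDD patients. That would treat Section 1.3 as the governing text, which the documents do not establish, and would remove eligible, treated patients from the main result.

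The reply that baseline tables will show the mix answers only part of the point: they show how many patients carry each diagnosis, not their outcomes.

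**Conclusion.** The point holds as a mismatch between population labels and eligibility, together with an analysis that cannot separate the groups. The text is clear that degenerative scoliosis without DDD is admitted, that the indication as written does not list it, and that one pooled rate is planned. The consequence is conditional: the rate *may* not describe the population named. It will not matter if no such patient is enrolled, and the numerical shift is nil if fusion does not depend on diagnosis.

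The ranges in the table rest entirely on the assumed rates and counts and should be read as illustration. The main harm is a possibly mislabelled estimate carried forward as pilot data. Because the remedy is nearly free, the change should be made.

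**What to change.** 1. **Section 10, results by diagnosis.** Keep the all-patient fusion rate and VAS/ODI results as the main summary. State that the same results will also be reported separately for (a) patients who meet the indication as written in Section 1.3, meaning DDD with or without Grade I spondylolisthesis, and (b) patients with degenerative scoliosis without DDD. Use the diagnosis recorded under Section 8.1, making sure the form shows whether DDD is present when scoliosis is entered.
2. **Labels.** Use on-label or DDD only for the group that each term fits, or confirm on-label against the full cleared indication and say so.
3. **Reconcile the population wording** in Sections 1.1, 1.3, 3.1, 3.2, 4.2 and 10. This point takes no position on which eligibility rule is right.

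The cost is one paragraph in Section 10 and aligned wording elsewhere, with no new data item. The small downside is that the group results will be imprecise. For example, an assumed 3 of 5 fused has an exact 95% interval of 14.7% to 94.7%. They should be presented descriptively, without a test between groups.

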### 1.2 Background

TLIF addresses a range of painful degenerative pathology including DDD and spondylolisthesis. PEEK cages are the standard of care for use in TLIF, however titanium cages have shown good results compared to PEEK in the literature.

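### Section 10 reports the primary fusion rate of 20 patients without an interval or a rule for 2-level patients, and cites no PEEK-specific source or figure for the PEEK comparison of Sections 2 and 3.1

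*Combined protocol and SAP*

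**What the plan says.** The primary endpoint (Section 3.3) is fusion status at 1 year. Its whole analysis is one sentence in Section 10: "The fusion rate will be reported and qualitatively compared to TLIF fusion rates in the literature", with a citation of reference 3. By its title in Section 11, reference 3 compares minimally invasive with open TLIF.

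Other sections bear on how that sentence is read:

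- **Unit.** Section 1.1 gives the aim as "To evaluate the fusion rate and clinical outcomes at 1 year of 20 patients with DDD who undergo a 1 or 2 level TLIF", and Section 3.2 says "20 patients requiring an open 1 or 2 level TLIF will make up the study population". Section 5.1 asks the investigator for an overall assessment of fusion and does not say how levels combine within a patient.
- **Comparator.** The hypothesis in Section 2 is that "TLIF fusion rate, adverse events and patient reported outcomes will be qualitatively comparable to PEEK results in the literature". Section 3.1 likewise sets the study against published outcomes of the PEEK cage. Section 1.2 states that "PEEK cages are the standard of care for use in TLIF" and cites reference 1, which by its title compares fusion rates with PEEK and titanium cages in TLIF. Section 10 does not cite reference 1.
- **Size.** Section 4.1 says "20 patients will be enrolled in the study", calls the study a pilot and gives no statement of precision.
- **Later use.** Section 1.1 adds: "It will also provide pilot data for future studies that will compare the Tritanium ® cage to PEEK".

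**The concern.** Three things that a reader needs in order to interpret the primary result are not fixed.

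- **Precision.** No interval is planned, and 20 patients leave a wide range of true rates. A bare 90% invites the reading that the cage matches PEEK, when the data would also fit a true rate near 70%.
- **Numerator and denominator.** Twenty patients with 1 or 2 treated levels give 20 to 40 levels. No rule covers a 2-level patient with partial fusion, and none defines who is evaluable at 12 months.
- **Benchmark.** No reference rate is written down, so *satisfactory* and *comparable* in Section 2 have no stated value behind them. The source attached to the comparison concerns surgical approach by its title, not cage material. By contrast, the same section sets numeric thresholds in advance for the secondary outcomes (2.8 for leg pain, 2.1 for back pain, 14.9 for ODI).

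The study's rate and the literature rate could therefore look alike or different for reasons unrelated to the cage. Whoever designs the later trial against PEEK would also inherit a figure without its uncertainty.

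**Working it through.** **Inputs.** Only n = 20 patients and 1 or 2 levels per patient come from the documents (Sections 3.2 and 4.1). The numbers fused, evaluable and with 2 levels are assumptions, shown as ranges. The plan gives no alpha, power, expected rate, margin or target precision, so there is no figure of its own to reproduce.

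**Step 1: precision of 20 patients.** The exact (Clopper-Pearson) 95% limits for x fused of n are:

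- lower = Beta quantile at 0.025 with parameters (x, n − x + 1)
- upper = Beta quantile at 0.975 with parameters (x + 1, n − x)
- for x = n, lower = 0.025^(1/n) and upper = 1; at n = 20, 0.025^(1/20) = 0.832

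| Fused / evaluable | Rate | Exact 95% interval | Width (points) |
|---|---|---|---|
| 17/20 | 85% | 62.1% to 96.8% | 34.7 |
| 18/20 | 90% | 68.3% to 98.8% | 30.5 |
| 19/20 | 95% | 75.1% to 99.9% | 24.7 |
| 20/20 | 100% | 83.2% to 100% | 16.8 |

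The width does not depend much on the choice of method: the Wilson interval for 18/20 is 69.9% to 97.2%.

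**Step 2: the denominator.** Suppose 18 patients have a gradable CT and 16 of them are fused. Among evaluable patients the rate is 16/18 = 88.9% (65.3% to 98.6%). With the two missing patients counted as not fused it is 16/20 = 80% (56.3% to 94.3%). The undefined word *evaluable* is worth 88.9 − 80.0 = 8.9 points here.

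**Step 3: the counting unit.** Let k patients have 2 levels, f levels fail, and d be the number of patients with at least one failed level.

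- per-level rate = (20 + k − f) / (20 + k)
- per-patient rate, all treated levels fused = (20 − d) / 20

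| k | f | d | Per level | Per patient | Patient minus level |
|---|---|---|---|---|---|
| 10 | 3 | 3 | 27/30 = 90.0% | 17/20 = 85.0% | −5.0 |
| 10 | 3 | 2 | 27/30 = 90.0% | 18/20 = 90.0% | 0.0 |
| 5 | 2 | 1 | 23/25 = 92.0% | 19/20 = 95.0% | +3.0 |

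The direction depends on the case mix and on whether failed levels share a patient.

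**Step 4: the comparator.** Sections 2 and 3.1 ask how the cage compares with PEEK. Section 10 answers with TLIF rates and reference 3. The two are compatible if TLIF rates stand in for PEEK, which the standard-of-care statement in Section 1.2 makes plausible. The plan does not say that this is the intention, and the documents do not show which cages the studies in reference 3 used.

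**The case against.** The strongest defence is that this is a declared pilot and case series with an explicitly qualitative comparison. No decision depends on a threshold, and anyone given the count and denominator can work out the interval. Much of this stands: the absence of a test, margin or power calculation is not an error. But a descriptive rate still needs a defined numerator and denominator, and a small sample makes the interval more informative, not less.

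A reader might infer three stronger points, which the documents do not support:

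- **That Section 10 contradicts Sections 2 and 3.1.** PEEK rates may fall within TLIF rates in the literature, and the cage mix behind reference 3 cannot be seen. The text has lost specificity; it is not in flat conflict.
- **That the literature source is left open until the CTs are read.** Section 10 already names one. What is absent is a PEEK-specific source and a figure taken from it in advance.
- **That counting levels flatters the cage.** Step 3 shows that the per-patient rate can be lower, equal or higher.

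It is also fair to say that Sections 1.1 and 5.1 lean towards the patient as the unit. They do not settle the patient with one fused level. Finally, with an interval about 30 points wide, many benchmarks will fall inside it. That limits what the comparison can show, and the plan should say so.

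**Conclusion.** The point holds in limited form. Followed as written, the plan would set an imprecise rate, with an undefined rule for partial fusion, beside a source not shown to address its PEEK question. The exact 95% interval is 16.8 to 34.7 points wide for 17 to 20 fused of 20. The unit of counting shifts the rate by −5.0 to +3.0 points in the scenarios shown, which is small beside that width and of no fixed sign. These figures rest on assumed counts, case mix and CT completeness.

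References 1 and 3 are judged by title only. The comparator part is therefore a request for clarification, while the missing interval and the missing 2-level rule are plain omissions. The change should be made; its absence is not fatal to a pilot.

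**What to change.** 1. **Section 10, estimate.** Report the number fused, the number evaluable and an exact (Clopper-Pearson) 95% interval per patient. Count a patient as fused only if all treated levels are fused. Define evaluable as having a gradable 12-month CT. For the analysis, count a patient with revision or device removal for non-union at the index level before then as not fused. State the number with missing CT and give the result with them counted as not fused.
2. **Section 10, benchmark.** Before the first 12-month CT is read, write in the fusion rate or range from a PEEK TLIF source, after checking its fusion definition, time point and counting unit. Reference 1 is a candidate by its title only; reference 3 may stay as a secondary source. If the chosen source counts levels, also report the per-level count and percentage, without an interval, because levels within a patient are not independent.
3. **Section 10, wording.** A benchmark inside the interval is *not contradicted*, not *shown comparable*. If it lies above the upper limit, the study rate is *lower than the literature value*; if below the lower limit, *higher than the literature value*. A range only partly inside is *inconclusive*. Add that the interval covers sampling error only, not the benchmark's own uncertainty or differences in how fusion is graded (Section 5.1 lists example signs without a threshold).
4. **Section 4.1.** State the precision of 20 patients: about 68% to 99% if 18 fuse.

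The cost is a few sentences, a check of one or more PEEK sources and a little more analysis. No test, margin, extra patients, readers, visits or imaging are needed. The downside is a more cautious conclusion.
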